#### **10.1.8.2. Audit and Inspection of Sites**

Participation by the investigator in this study implies acceptance of potential inspection by government regulatory authorities and applicable institutional compliance and quality assurance offices. During the conduct of the study, Corbus may conduct audits of any data and facility participating in the study. The investigators and institutions involved in the study will permit

such study-related audits and provide direct access to all paper study records not contained within the electronic medical record or eCRFs and to the facilities. The investigator must maintain a comprehensive and centralized filing system of all study-related documentation that is not part of the electronic medical record or eCRFs and that is suitable for inspection by Corbus or its designated site monitors, Quality Assurance monitors, EC representatives, and representatives of government regulatory bodies. The investigators agree to participate in audits conducted at a convenient time in a reasonable manner.

Government regulatory authorities or representatives from ECs may also perform inspections either during or after the study. In the event of an inspection by any regulatory authority, the investigators will promptly notify Corbus and will allow Corbus representatives to be present during the audit, if permitted by the regulatory authority and institutional policy. The investigators agree to cooperate fully with inspections conducted by regulatory authorities and to allow representatives of the regulatory authority access to all study records. The investigator will forward to Corbus a copy of any inspection records received.

### **10.1.9. Data Handling and Record Keeping**

#### **10.1.9.1. Data Handling, De-Identification and Source Records**

The investigators and designees will maintain appropriate records for this study, in compliance with ICH E6, Section 4.9 and regulatory and institutional requirements for the protection of confidentiality of subjects. All study records will be maintained in accordance with Corbus' policies and applicable regulatory requirements. There may be circumstances for which Corbus is required to maintain study records and, therefore, Corbus should be contacted before removing study records for any reason.

Source data/records contain all the information, which is necessary for the reconstruction and evaluation of the study. The primary source document for this study will be the subject's medical record on site stored in paper form or in an electronic medical record. If separate research records are maintained by the investigator, both the medical records and the research records will be considered the source documents for the purposes of auditing the study. Data recorded on source documents will be transcribed by site staff onto eCRFs provided by Corbus or its designee.

In addition, in this study at the time of the office visit, study-specific original data elements such as responses to questionnaires may be entered directly into an electronic system without first being transcribed on other media such as paper. There will be no separate source document for data entered directly into the electronic system.

Source data/records are: 1) original records; 2) certified copies of original records; 3) observations; 4) laboratory reports; and 5) eCRFs and/or data sheets. Source data/records are to be kept by the investigator until the end of the regulatory retention period. All clinical findings, observations, laboratory results, subject correspondence, SAE reports, and other information related to subject participation in the study must be maintained in subject binders that contain source documents and other data collection instruments designed specifically for this investigation. Completed eCRF pages will be reviewed by Corbus or Corbus authorized personnel.

The investigator will permit study-related monitoring, audit(s), EC review(s) and regulatory inspection(s), with direct access to all the required source documents. Site staff will permit authorized representatives of Corbus, EC and government regulatory agencies to examine (and when required by applicable law, to copy) study records for the purposes of quality assurance reviews, audits, and evaluation of the study safety, progress and data validity.

#### **10.1.9.2. Original Records**

Clinical trial data will be recorded on source documentation and entered by the investigator or a qualified designee into a validated 21 CFR Part 11 compliant internet-based EDC system. Changes to the clinical trial data can only be performed by the investigator or qualified designee through the change management methodology that is subject to a full audit trail.

The investigators and qualified designees should be trained on the EDC system before enrollment of the first subject at their site. A list of the status of each user, including an audit trail of status changes, will be maintained.

At the end of the study, the completed eCRF must be reviewed and signed electronically by the investigator or a co-investigator authorized to sign. A certification must be obtained from all authorized persons to sign electronically indicating that their electronic signature is equivalent to their hand-written signature.

#### **10.1.9.3. Confidentiality of Subject Data**

To maintain subject confidentiality, subjects will not be identified by name, subjects will be assigned a site number and subject number for any documentation submitted to Corbus. Additional subject confidentiality issues, if applicable, are covered in accordance with each participating country, and institution's laws, regulations and policies.

#### **10.1.9.4. Data Collection and Management Responsibilities**

Data collection and accurate documentation are the responsibility of the investigator and site staff under the supervision of the investigator. All source documents and laboratory reports must be reviewed by the study team and data entry staff, who will ensure that they are accurate and complete. A site monitor for Corbus will ensure the data are collected and maintained correctly and in compliance with [Section 10.1.8.1](#).

Electronic data capture on eCRFs will be used, using internet access with password protection and data quality checks. It is expected that the eCRFs should be submitted coincident with the subject visit or within 5 business days.

A Data Monitoring Plan will be created to specifically identify how data management will be performed for the study. The following summarizes this plan:

- The clinical database will be held and managed by an EDC vendor. The EDC will be used for online edit checks, batch edit checks and query management
- A Data Validation Plan will be created which will include the specifications for:
  - Online checks performed by the EDC system during data entry
  - Batch edit checks

- Manual checks performed by the site monitor, Medical Monitor data management, and/or other study team personnel
- Other data cleaning activities such as data reconciliation and coding listing reviews will be performed.

Queries are handled within the EDC application where the monitors and data managers can generate a query. Under direction of the investigator, the site team addresses the query. If the query is due to a data entry error, the site staff can immediately make the corrections in the applicable eCRF pages. If the query needs clarification, the site staff contacts the investigator for resolution. The site coordinator then enters the correct value or submits an answer to the query without modifying the data. The monitor or data managers then review the corrected eCRF pages and/or answer. If the data are changed correctly or the answer is acceptable, the monitor or data manager closes the query. If the answer is not acceptable, the monitor or data manager submits an additional query for clarification. All changes to the database require a “Reason for Change” and are subject to an audit trail. The audit trails identify the changed data, reason(s) for change, who changed the data, and the time and date of the change.

Centralized monitoring will be performed daily or at an agreed-upon frequency, as defined in the Data Monitoring Plan. The sites will receive feedback about data quality and data management issues at their own sites. Corrective actions will be implemented as necessary.

Routine EDC management reports will be available to view the data for consistency. Additional management reports will be obtained and reviewed, as indicated during the study.

#### **10.1.9.4.1. Trial Master File**

The Trial Master File for Corbus will be maintained within an electronic document storage system using 21 CFR Part 11 compliant software.

#### **10.1.9.5. Study Records Retention**

The investigator must ensure that the following records and documents pertaining to the conduct of the study and the distribution of study product are retained for as long as needed to comply with national and international regulations (generally 2 years after discontinuing clinical development or after the last marketing approval): copies of the study specific documents and other sources of information such as original medical documents, data and records (such as hospital records, clinical and office charts, laboratory notes, memoranda, documents regarding subject treatment and study product accountability, and original signed ICFs). All EC records related to this study will be retained by the site for as long as required by the local EC.

In the event the investigator retires, relocates or for any other reason withdraws from the responsibility for maintaining records for the time required, custody of the records may be transferred to any other qualified person who will accept responsibility for the records. Notice of such a transfer must be given in writing to Corbus. The investigator must contact Corbus before disposal of any records related to this study.

#### **10.1.10. Protocol Deviations**

The investigator should not implement any deviation from or changes of the protocol without agreement by Corbus and prior review and documented approval from the reviewing EC, except

where necessary to eliminate an immediate hazard to trial subjects or when the change involves only logistical or administrative aspects of the trial (e.g., change in monitor[s], change of telephone number[s]).

The investigators and site staff are responsible to follow the written protocol as provided by Corbus and approved by their EC.

A protocol deviation is an excursion from the protocol that is not implemented or intended as a systematic change and that has not received prior approval by the reviewing EC. There are several types of protocol deviations with different requirements for reporting each type of deviation.

An emergency protocol deviation occurs in an emergency when an excursion from the protocol is required to protect the life or physical well-being of a subject. The medical monitor and the reviewing EC must be notified as soon as possible, but not later than 5 days after the emergency occurred. The medical monitor will be notified through the EDC system. Relevant regulatory agencies will be notified according to their timelines for reporting.

A major protocol deviation occurs in a non-emergency when the subject, investigator or Corbus fails to adhere to significant protocol requirements affecting the inclusion, exclusion, subject safety or primary endpoint criteria. Major protocol violations for this study include but are not limited to any of the following:

- Failure to comply with GCP guidelines
- Failure to meet eligibility criteria at randomization
- Use of a prohibited concomitant medication
- Failure to obtain all TIS core set measurements at Visit 1 or Visit 10
- Failure to report AE/SAE in a timely manner

Major protocol deviations must be reported to Corbus electronically in the manner specified within 5 days of the first time the investigator or site staff becomes aware of the deviation and must be reported to the EC within that EC's guidelines. Corbus will determine if an emergency or major protocol violation should result in early discontinuation of study treatment for a subject.

A copy of the Major Protocol Deviation Form will be filed in the site's regulatory binder and in Corbus' files. The site will report the violation to their EC in accordance with their EC reporting requirements.

A minor or administrative protocol deviation is an excursion from the protocol that does not affect the scientific soundness of the research plan or the rights, safety, or welfare of human subjects. Examples of minor or administrative deviations could include: follow-up visits that occurred outside the protocol required time frame because of the subject's schedule or blood samples obtained at times close to but not precisely at the time points specified in the protocol. If a protocol deviation occurs which meets this definition, the deviation should be reported to the reviewing EC (if reporting is required) at the time stipulated such as when the continuing review application is submitted. These minor or administrative deviations will be reported by the investigator or designee in the specified manner within 28 days after their occurrence.

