### **3.1.2. Part B: Optional Open-label Extension**

Upon completing Part A (Visit 10), at the investigator's discretion, consenting subjects may directly rollover into the optional OLE Phase (Part B). All subjects in the OLE will receive lenabasum 20 mg BID (see [Table 4](#)).

Subjects will continue their standard of care treatment as in Part A. Subject's corticosteroid or other immunosuppressant treatments may be reduced during this study if the investigator determines that clinical improvement in the subject's dermatomyositis has occurred and a reduction is warranted. A preferred schedule for reduction of corticosteroid is provided in [Section 5.5.1](#).

The OLE may be extended beyond 1 year. Sites will be notified by an administrative memo as to any extension and will inform their EC/IRB. The design of an extended OLE will follow the same design and procedures as described in Table 4. At the investigator's discretion, consenting subjects will rollover at the conclusion of Visit B8. The extension visits will be captured in the electronic data capture (EDC) as C1-C8 respectively.

Subjects who discontinue the study at any stage and for any reason will be encouraged to complete the procedures described in the Early Termination (ET) Visit as well as complete the Safety Follow-up Visit  $4 \pm 1$  weeks later.

The same efficacy and safety parameters described as primary and secondary objective for Part A will be evaluated in Part B as described in the SAP.

The results of Part B are expected to be analyzed after Part A results have been completed and will be reported as either an addendum to the clinical study report (CSR) or as a separate CSR.

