#### **5.5.1. Guidelines for Reduction in Concurrent Immunosuppressant Medications including Corticosteroids**

For both Part A and Part B, doses of concurrent immunosuppressive medications including oral corticosteroids may be reduced during the study at the discretion of the investigator. Appropriate reasons for reduction would be AEs or intolerance related to the immunosuppressant medication or clinical improvement in DM during the study. These general principles should be observed for dose reduction in immunosuppressant medications:

- A reduction in immunosuppressant medications can be done at any time during the study for AEs or tolerability concerns related to that immunosuppressant medication.

Subjects who require a reduction in concurrent immunosuppressive medications for safety or tolerability reasons will have their doses adjusted at the investigator's discretion.

- *Part A only:* A subject's immunosuppressant medications (including oral corticosteroids) may be reduced between Visits 4-8 if the investigator determines that clinical improvement in the subject's DM has occurred and a reduction is warranted.
- *Part A only:* No reduction in immunosuppressive medications (including oral corticosteroids) should be done between Visits 9 and 10, except for reasons of safety and tolerability. This provides approximately 12 weeks of stability on medications before assessment of the primary efficacy outcome.
- Dose reduction in oral corticosteroids should occur before dose reduction in non-corticosteroid medications. It is recommended that doses of non-corticosteroid immunosuppressive medications are reduced only if average daily oral corticosteroid dose is  $\leq$  5 mg prednisone or equivalent.
- Dose reduction in chronic oral corticosteroids generally should be gradual with progressive decrements at intervals of no less than 4 weeks. The recommended schedule for reduction in chronic corticosteroids dose provided in Table 2.

**Table 2 Recommended Schedule for Reduction in Chronic Oral Corticosteroid Dose When Determined by the Investigator to be Appropriate at Visits 4-8**

Daily oral prednisone dose or equivalent at time of visit	Reduction in daily oral prednisone dose or equivalent
> 15 mg	5 mg
> 5 mg to $\leq$ 15 mg	2.5 mg
$\leq$ 5 mg	Investigator decision for 2.5 mg or discontinue corticosteroids completely

A non-exhaustive conversion table of frequently used corticosteroids and dosage is found in [Appendix 7](#).

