## **6. DISCONTINUATION OF STUDY TREATMENT, SUBJECT WITHDRAWAL, AND EARLY TERMINATION**

### **6.1. Discontinuation of Study Treatment and Subject Withdrawal**

Subjects are free to withdraw from participation in the study at any time upon request.

A subject will not receive any further study product if any of the following events occur:

- Subject lost to follow-up
- Withdrawal of consent for study participation
- Subject decision to discontinue treatment
- Pregnancy
- Any serious or life-threatening AE probably or definitely-related to lenabasum
- Any AE, which in the opinion of investigator, can jeopardize the safety of an individual subject
- Subjects recognized as being treated despite being wrongly randomized (i.e., not meeting all eligibility criteria)
- Other event(s) which in the opinion of the site investigator or Medical Monitor contraindicates further dosing such as, but not limited to, repeated failure to meet protocol requirements, significant concurrent illnesses or disease complications

Subjects withdrawn for the above reasons, except lost to follow-up or withdrawn consent, will be asked to return to Visit 4, Visit 6, Visit 8 (if they have not already had Visit 4, 6, and 8), and Visit 10; Weeks 16, 28, 40 and 52, respectively. These subjects will not be required to but may undergo optional blood sampling, skin photography, or skin biopsies at the remaining visits if they had opted in previously.

Subjects who are discontinued permanently from drug therapy due to an AE related to study product will be followed until resolution or stabilization of the event. Subjects who are withdrawn due to pregnancy, or partners of subjects who become pregnant, will require additional follow-up as outlined in Pregnancies, [Section 8.2.7.8](#).

Subjects who withdraw consent will be asked to complete the early termination (ET) visit; however, completion of the visit will not be mandated.

A subject will be considered lost to follow-up if he/she does not respond to the following:

- Three attempts at contacting the subjects (including phone calls, emails, or texts and a certified letter) from a member of the research staff over a period of up to a month;
- A certified letter updating him/her on the study status.

Documentation of the contact attempts and the certified letter should be filed with the subject's source documents.

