### 9.3. Populations for Analyses

There are 4 analysis populations defined in this study:

**The modified intent to treat (mITT) population** will consist of all randomized subjects who have received at least one dose of study product. Analysis of the modified ITT population will be used as the primary efficacy analyses and will analyze subjects under the treatment to which they were randomized, regardless of compliance with assigned treatment.

**The per protocol (PP) population** will consist of subjects who complete the study without major protocol violations deemed likely to affect the efficacy outcomes of interest (these deviations will be classified during a blinded deviation review meeting before unblinding the study). Analysis on the PP population will be used as secondary efficacy analyses, analyzing subjects under the treatment actually received.

**The safety population (SAF)** will consist of all subjects who received any study product. Analysis performed on the safety population will be according to the treatment actually received.

**The pharmacokinetic (PK) population** will consist of all subjects from the SAF whose pharmacokinetic data are adequate for the calculation of primary PK parameters. Inclusion in the PK population of subjects with missing data or protocol violations or inadequate dosing will be considered on a case-by-case basis. The PK population will be the analysis set used for all pharmacokinetic analyses.

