#### **9.4.1.1. Handling of Missing Data**

The analysis of the primary endpoint will be performed on the mITT population, using a mixed-effect model for repeated measures (MMRM), on observed data, using last observation carried forward (LOCF) for  $\leq 2$  missing core set items. If more than 2 core items are missing, the TIS score will not be calculated for that visit. Sensitivity analyses for the primary endpoint will include imputing missing data using last observation carried forward, the completer population, and the per-protocol population.

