#### **9.4.2. Analysis of the Primary Efficacy Endpoint(s)**

The primary efficacy variable is the TIS. The primary analysis is to compare the TIS at Week 28 between the lenabasum 20 mg BID treated group and placebo using a mixed model for repeated measures (MMRM). The model will have TIS score as a dependent variable, treatment, visit, treatment\*visit interaction, baseline MMT-8 score, baseline prednisone use, and region as fixed factors, and subject as a repeated random effect. The model may incorporate other baseline factors as covariates, which will be further defined in the statistical analysis plan. Two-sided p-values and 95% confidence intervals associated with the least-square (LS) mean difference between the lenabasum group and placebo will be presented for each visit. If the distribution of the TIS score does not meet the assumptions of normality, a nonparametric analysis may be performed (e.g., MMRM analysis on the ranked data).

Two-sided p-values and 95% confidence intervals associated with the least-square (LS) mean difference between the lenabasum group and placebo will be presented for each visit.

Because TIS is a composite score, absolute values and change from Baseline in each core set measure will be presented to support the primary efficacy endpoint.

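### The per-protocol set and the listed TIS deviation are tied to Week 52, but the primary endpoint is TIS at Week 28

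*Protocol*

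**What the plan says.** - **Endpoint.** Section 9.4.2: "The primary analysis is to compare the TIS at Week 28 between the lenabasum 20 mg BID treated group and placebo". Table 3 and Section 6.1 put Week 28 at Visit 6, Week 40 at Visit 8 and Week 52 at Visit 10. TIS at Week 52 is a secondary endpoint (Section 9.4.3).
- **Deviation list.** Section 10.1.10 defines a major deviation as a failure on significant requirements "affecting the inclusion, exclusion, subject safety or primary endpoint criteria". It then gives a non-exhaustive list whose only TIS entry is "Failure to obtain all TIS core set measurements at Visit 1 or Visit 10".
- **PP set.** Section 9.3: PP "will consist of subjects who complete the study without major protocol violations deemed likely to affect the efficacy outcomes of interest". The deviations are classified in a blinded review before unblinding.
- **Completion.** Section 3.1.2 begins "Upon completing Part A (Visit 10", which places the end of Part A at Week 52. The synopsis expects 120 subjects to complete the study. Section 9.2 expects the same 120 to complete at least Week 28. Both assume about 20% dropout.
- **Use of PP.** Section 9.4.1.1 lists, among the sensitivity analyses for the primary endpoint, "the completer population, and the per-protocol population".
- **Background medication.** Section 5.5.1 allows reductions for clinical improvement at Visits 4–8 and, safety and tolerability apart, none between Visits 9 and 10. Its reason: "This provides approximately 12 weeks of stability on medications before assessment of the primary efficacy outcome".

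**The concern.** A PP analysis of a Week 28 endpoint should depend on what happened up to Week 28. Here membership depends on staying to Week 52. A subject with complete, valid Week 28 data who withdraws consent or is lost to follow-up at, say, Week 40 is removed from the Week 28 PP comparison. If PP and mITT then disagree, the reader cannot tell whether adherence up to Week 28 or later dropout is the cause, so PP no longer tests the robustness of the primary result cleanly.

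The deviation list has the same late anchor. It names baseline and a secondary visit and omits the visit of the primary endpoint. Sites must report major deviations to the sponsor within 5 days, so the list guides what they flag. It points them to Visit 10 and does not name Visit 6.

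**Working it through.** **1. Timing.** The primary endpoint is at Visit 6 = Week 28. The listed TIS deviation names Visit 10 = Week 52. Completion of Part A is at Visit 10 = Week 52. The gap is 52 − 28 = 24 weeks.

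Section 5.5.1 is a further sign of the Visit 10 anchor. Counting 12 weeks back from Week 52 gives 52 − 12 = Week 40 = Visit 8, the end of the reduction window. The statement therefore fits a Week 52 primary outcome. Week 28 lies inside the Visit 4–8 window (Weeks 16–40).

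**2. The plan's own power figure.** Inputs from the synopsis: difference 15, SD 20, two-sided alpha 0.05, 48 completers per compared arm. SE = 20 × √(2/48) = 4.08, and 15/4.08 = 3.67. Power is 95.7% by the normal approximation and 95.3% by the t-test. The stated 95% reproduces.

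**3. Cost in PP.** The protocol gives no loss rate between Weeks 28 and 52. Assume 5–20% of the 48 per arm leave in that interval: 0.05 × 48 = 2.4 and 0.20 × 48 = 9.6 per arm. With SE = 20 × √(2/n):

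| Assumed late loss | n per arm | SE (TIS points) | Power, t-test | Power, normal |
|---|---|---|---|---|
| 0% | 48 | 4.08 | 95.3% | 95.7% |
| 5% | 46 | 4.17 | 94.5% | 94.9% |
| 10% | 43 | 4.31 | 93.0% | 93.5% |
| 20% | 38 | 4.59 | 89.7% | 90.5% |

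These figures are before any exclusion for protocol violations.

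**4. Is 5–20% plausible on the plan's own dropout figure?** Assume a constant dropout hazard and take each reading of the 20% in turn.

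- *20% lost by Week 52 (synopsis).* Loss by Week 28 is 1 − 0.8^(28/52) = 11.3%. About 150 × 0.887 = 133 reach Week 28, and 133 − 120 = 13 of them (9.8%) leave later.
- *20% lost by Week 28 (Section 9.2).* Loss by Week 52 is 1 − 0.8^(52/28) = 33.9%. About 150 × 0.661 = 99 complete, and 120 − 99 = 21 of the 120 (about 17%) leave later.

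Both fall inside the assumed range. These counts are upper limits for the subjects affected if some of the dropouts stop study product only and still attend.

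**5. Possible shift in the PP estimate.** Suppose leavers score d points lower at Week 28 than stayers, with the same d in both arms. Dropping a fraction f of an arm raises that arm's mean by d × f. The treatment difference moves by d × (difference in f between arms). With d = 10 (assumed) and equal loss, 10 × 0 = 0. With a 5-percentage-point imbalance (assumed), 10 × 0.05 = 0.5 point.

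**The case against.** **The deviation item excludes nobody by itself.** The list is not exhaustive, the general definition already covers primary endpoint criteria, and the blinded review excludes only for violations likely to affect efficacy. A missing Visit 10 measure cannot alter a Week 28 value, and Week 52 TIS is a ranked secondary endpoint, so naming Visit 10 is not in itself wrong. All of this stands. A missing Visit 6 measure can still be caught. What remains is that the list does not name the primary-endpoint visit.

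**Completion is not defined for the individual subject.** Section 3.1.2 concerns rollover to Part B, and Section 9.2 counts completion at Week 28, so a Week 28 reading is possible. It is the less natural reading of Section 9.3, given a 52-week Part A. The blinded review classifies deviations and does not lift the separate completion condition.

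**Few subjects are affected.** Section 6.1 says that those who stop study product "will be asked to return to Visit 4, Visit 6, Visit 8" and Visit 10, except subjects lost to follow-up or withdrawing consent. That is right, and it narrows the group to those who leave the study.

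**The effect is small and rests on assumed rates.** Also right. PP is not the powered analysis, and a 0.5-point shift is small beside an SE above 4. The harm is mainly to interpretation.

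**The completer set has no stated anchor.** True: Section 9.3 does not define it. Fixing it at Week 28 fills in detail, and the finding does not depend on it.

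**Conclusion.** The concern holds and should be fixed. Read as written, the PP rule conditions a named sensitivity analysis of the Week 28 endpoint on retention to Week 52, and the deviation list omits the primary-endpoint visit. The Visit 10 anchor recurs in Section 5.5.1, and the synopsis and Section 9.2 give two meanings of completion for the same 120 subjects.

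Under an assumed late loss of 5–20%, PP loses about 2–10 subjects per compared arm, its power drops by roughly 1 to 6 percentage points, and the SE rises from 4.08 to 4.17–4.59. Any shift in the estimate depends on unequal late loss between arms and cannot be sized from the protocol. The primary mITT analysis, alpha, testing order and sample size do not change.

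**What to change.** - **Section 10.1.10:** list missing TIS core set measures at Visit 1, Visit 6 or Visit 10.
- **Section 9.3:** define PP for the primary endpoint by completion through Visit 6 (Week 28), counting only relevant deviations up to that visit. Keep a Visit 10 version for the Week 52 endpoint.
- **Section 9.4.1.1:** state that the completer set for the primary endpoint means completion through Week 28.
- **Synopsis and Section 9.2:** use one meaning of completion for the 120 subjects and the 20% dropout.
- **Section 5.5.1:** reconcile the statement about when the primary outcome is assessed with Week 28. No change to any medication rule is proposed here.

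These are wording changes and need no added patients or assessments. They do have to pass through a protocol amendment with ethics committee review (Section 10.1.2). Naming Visit 6 also makes a missed core measure there an explicitly listed major deviation, with its 5-day reporting.
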